4.4 Serious adverse events

An SAE is any untoward medical occurrence that at any dose:

- Results in death
- Is life-threatening (i.e., the subject was, in the opinion of the investigator, at immediate risk of death at the time of the event, it does not refer to an event that hypothetically might have caused death if more severe)
- Requires inpatient hospitalization or prolongation of existing hospitalization
- Results in persistent or significant disability/incapacity
- Is a congenital anomaly/birth defect
- Is an important medical event that might not be immediately life threatening or result in death or hospitalization but might jeopardize the subject or might require intervention to prevent one of the other outcomes listed above. Examples of such events are intensive treatment in an emergency room or at home for allergic bronchospasm, blood dyscrasias or convulsions that do not result in hospitalization or development of dependency or abuse.

In general, hospitalization signifies that the participant has been detained (usually involving at least an overnight stay) at the hospital for observation and/or treatment that would not have been appropriate in the physician's office or outpatient setting.

Emergency room visits that do not result in hospitalization should be evaluated for one of the other serious outcomes to determine whether they qualify as SAEs.

4.5 Medication error

Medication error refers to any unintended error in the dosing and/or administration of the study drug as per instructions in the prescribing information. Medication errors generally fall into 4 categories as follows:

- Wrong drug
- Wrong dose (including dosing regimen, strength, form, concentration, amount);
- Wrong route of administration;

- Wrong subject (i.e. not administered to the intended subject).

Medication Errors include occurrences of overdose and underdose of the study drug.

4.6 Procedure for collection of adverse events and serious adverse events

All nonserious AEs and SAEs that occur in a subject from the time he or she signs the ICF until the final follow-up visit will be assessed and recorded on the source documents and CRF, regardless of causal relationship to the study drug.

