2.1 Overview

This study will employ a “pre-post” pragmatic design, which will consist of both a pre-period, or an observational baseline period, and a post-period, or an interventional period (Figure 1). During the pre-period, each participating site will implement the first component of the critical pathway through implementation of guideline-based criteria to identify patients at the point of care in the ED, obtain informed consent, and monitor enrolled subjects. Sites will initiate treatment for ABSSSI with “usual care,” defined as site- or physician-specific antibiotic treatment of ABSSSI with coverage for a known or suspected Gram-positive infection (e.g., vancomycin, linezolid, and daptomycin) to each study subject who meets all inclusion and exclusion criteria. Blinding of treating physician to subject enrollment in the study during the pre-period will ensure unbiased provision of usual care. During the “post” period, for all subjects who provide informed consent and are subsequently enrolled, each participating site will additionally implement the second component of the new critical pathway, use of dalbavancin, at the point of care in the ED to each study subject who meets all inclusion and exclusion criteria.

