2.3.1 Pre-period

During the pre-period, the study coordinator and/or other study nurses will identify patients who may be eligible for the study. All hospital staff may be reminded (through posters or memorandums) to inform the study coordinator and/or other study nurses as soon as an ABSSSI patient is seen in the ED. The study coordinator will implement inclusion and exclusion criteria for the new critical pathway by patient interview and/or chart review. Inclusion criteria includes measurement of lesion size through a physician assessment (Appendix A), and clinical judgment that patient requires coverage for a known or suspected Gram-positive infection. Patients who meet all inclusion criteria and none of the exclusion criteria based on study coordinator assessment will be enrolled in the study or flagged for further review by core study team physicians, who will make the final enrollment decision. The treating physician will be blinded to protocol content and study enrollment decision. Study coordinator will then complete all additional elements of enrollment, including informed consent, and scheduling of follow-up.

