3.2.2 Patient Diary Aid

Patients will be provided with a bound, paper diary to record specific information about their health status on days in which they have an interaction with a health care provider. The diary is intended only as an aid to help patients remember details about health care appointments, medications, and medical tests. The diary will not be collected by or returned to study staff.

4 Safety assessments

At each visit, subjects are to be queried regarding any adverse events (AEs) or serious adverse events (SAEs) that have occurred since the previous visit. Subjects will be asked to volunteer information with a nonleading question such as, “How do you feel since your last visit?” Study site personnel will record all pertinent information in the subject’s CRF. All AEs will be recorded on the appropriate AE reporting page of the subject’s CRF whether or not they are considered causally related to the study drug (any antibiotic given for ABSSSI from enrollment, including the pre-period).

For every AE, the investigator will:

- Provide an assessment of the seriousness of the event (i.e., is it an SAE?), as well as the severity and causal relationship
- Document all actions taken with regard to the study drug
- Detail any other treatment measures taken for the AE
- Document the outcome of the AE

In addition, subjects will be reminded, as described in the ICF to notify site personnel of any AEs occurring from the time the subject signed the ICF until the final follow-up visit. Any AEs that are ongoing at the time of the final protocol-defined study visit will be followed until the condition returns to pre-study status, has resolved or stabilized, or can be explained as being unrelated to the study drug. If a follow-up visit is deemed necessary for appropriate safety surveillance, it will take place within 30 days of the final protocol-defined study visit.

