7.3 Informed consent procedures

Patients, after being given an explanation of the study, will give voluntary and written informed consent and HIPAA (Health Insurance Portability and Accountability Act of 1996) authorization (in compliance with 21 CFR, Parts 50 and 312) or other appropriate documentation, according to local regulatory requirements, before participating in any study-related procedures.

Informed consent will be obtained from each subject prior to the beginning of any study-specific activities, and will include consent to collection of clinical, economic and humanistic outcomes. This may involve gathering data through chart review or directly eliciting information from subjects. Informed consent during the post-period, or interventional period, will involve consent to treatment through a new critical pathway. Each eligible subject will have the opportunity to read and review the approved informed consent form (ICF) and have the opportunity to ask questions to the participating Study Investigator, Study Coordinator, or other study team member. Signed copies of the ICF and the HIPAA or other locally applicable form will be given to the subject, and both documents will be placed in the investigator's study files.

The participating subject may withdraw participation and/or informed consent at any time throughout the conduct of the study. Withdrawing participation or consent will relieve the subject from any future data collection time points.

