6.2.10 Safety Assessments

The reporting period for adverse events (AEs) begins from the time of the signing of the Patient Authorization throughout the patient's enrollment in the study. AE information will be collected in an ongoing fashion through patient reporting AEs to their healthcare provider.

All AEs will be coded and summarized by the pre-period and post-period for the FAS population by system organ class and preferred term based on the MedDRA coding dictionary Version 20.0 or later; the most current MedDRA coding dictionary will be used at the time of analysis. AEs will be summarized by relationship to treatment as yes, there is evidence to suggest a causal relationship between the study drug (any antibiotic given for ABSSSI from enrollment, including the pre-period or post-period) and adverse event, and no, there is no evidence to suggest a causal relationship between the study drug and adverse event. For severity, the most severe case of an AE by a patient will be reported, with order of most severity as: Severe>Moderate>Mild.

A listing of adverse events will also be given for each patient and will include the reported term, seriousness, severity, relationship to treatment, action taken with medication, event outcome and date for each event reported.

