Appendix B: Derived Variables

Analysis Section (Visit)	Variable (Units)	Definition
General (Baseline)	Enrollment date	Informed consent date
General (Baseline)	Baseline date	Initial ED admission date
General (Initial Care)	Initial care indicator	If enrollment date \leq date \leq enrollment date + 13 days then = Yes Else = No
General (Follow-up)	Follow-up indicator	If enrollment date + 14 \leq date \leq enrollment date + 43 days then = Yes Else = No
Demographics (Baseline)	Age (years)	Round down to nearest integer((Initial ED admission date - date of birth + 1)/365.25), when both dates are available.
Demographics (Baseline)	BMI	weight (kg)/ [height(m)] ² Where necessary, height and weight will be converted to proper units.
Infection Characteristics (Baseline)	CCI	Will be scored as described in Appendix C. Includes variables for raw score and 10 year survival probability.
Infection Characteristics (Baseline)	Fever	If temperature > 38 ° C then =Yes Else =No
Infection Characteristics (Baseline)	Morbid Obesity	If baseline BMI \geq 40 then =Yes Else =No
Infection Characteristics (Baseline)	SIRS Criteria Met	SIRS criteria include abnormalities in temperature, heart rate, respiration, and white blood cell count. Specifically included are: 
 Fever of more than > 38.0°C or hypothermia with temperature < 36.0°C

[figure not shown]
[figure not shown]
Analysis Section (Visit)	Variable (Units)	Definition
		
 • Tachycardia with heart rate > 90 beats/minute or • Tachypnea with respiratory rate of > 20 breaths/minute or PaCO₂ of less than 32mmHg • Abnormal white blood cell count: leukocytosis >12,000/microliter, leucopenia <4,000/microliter, or >10% immature cells (bands).^{3,4} 
If 2 or more criteria present = Yes Else = No

Antibiotic Medications (Initial Care and Follow-up)	Days Received Antibiotic Medication	
Σ (Medication end date – Medication start date +1), when both dates are available. If dates overlap (e.g., end date and next start date are identical) then subtract 1 from summation for each occurrence.

Primary Outcome	Hospital Admission At Initial Episode of Care	
If discharge destination from the initial episode of care = Hospital and the reported hospitalization where discharge date = hospital date is infection-related then = Yes, Else = No

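### Adverse-event capture starts at consent in both periods, so reactions to the first usual-care dose can be missed in the pre-period, while reactions to dalbavancin cannot

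*Protocol*

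**What the plan says.** **Window.** Protocol 4.6 records "All nonserious AEs and SAEs that occur in a subject from the time he or she signs the ICF until the final follow-up visit". SAP 6.2.10 agrees: "The reporting period for adverse events (AEs) begins from the time of the signing of the Patient Authorization throughout the patient's enrollment in the study". Neither distinguishes the two periods.

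**Study drug.** Protocol section 4 (Safety assessments) defines it as "any antibiotic given for ABSSSI from enrollment, including the pre-period". SAP Appendix B sets the enrollment date to the "Informed consent date", which is a date without a clock time.

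**Post-period order.** Protocol 2.1 says that "for all subjects who provide informed consent and are subsequently enrolled, each participating site will additionally implement the second component", which is dalbavancin. Protocol 7.3 adds: "Informed consent during the post-period, or interventional period, will involve consent to treatment through a new critical pathway".

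**Pre-period order.** Under Protocol 2.3.1 the treating physician is blinded to the protocol's content and to the enrollment decision. The coordinator screens the patient and may refer the case to core-team physicians. After that: "Study coordinator will then complete all additional elements of enrollment, including informed consent, and scheduling of follow-up". Protocol 2.3.3 only anticipates that enrollment and treatment start share a date.

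**Use.** SAEs are a secondary outcome. SAP Tables 14 and 19–23 report AEs and SAEs for the full analysis set, summarised by period under SAP 6.2.10 without formal testing of SAEs.

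**The concern.** A comparison of harms between periods needs observation to start at the same point relative to treatment. Here it starts at a signature. In the post-period that signature precedes study treatment by design. In the pre-period nothing visible ties it to the first dose, and a prescriber who does not know the enrollment decision has no protocol reason to wait for it.

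If some pre-period subjects received their first antibiotic before signing, a reaction in that interval lies outside the window, while the same reaction to dalbavancin would be recorded. The error can run only one way for each period's own study treatment: usual care looks safer and dalbavancin, by comparison, worse. No planned output shows the order of consent and first dose, so a reader of the tables could not tell whether this had happened.

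**Working it through.** The plan states no figure on this point, so there is none to reproduce. The check is a reading of the sequence, followed by an illustration under assumed inputs.

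**Step 1: sequence by period**

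| | Pre-period | Post-period |
|---|---|---|
| Capture starts | ICF signature | ICF signature |
| Who starts treatment | Physician blinded to enrollment | Site, for consented and enrolled subjects |
| Consent required before first study treatment? | Not stated | Yes |
| Dose-to-consent gap possible for study treatment? | Yes | No |

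Protocol 7.3 requires consent before study-specific activities, but does not say that usual care in an observational period is one. SAP 6.1.1 requires at least one antibiotic dose for the pre-period full analysis set and gives no timing relative to consent. No passage extends capture back to the first dose.

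**Step 2: absolute size (illustration)**

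Let *d* be the share of pre-period subjects dosed before consent and *r* the rate of first-dose reactions, all taken to occur before consent (the worst case). The documents give neither. With 161 subjects per period (Protocol 5.3):

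- expected number missed = 161 × *r* × *d*
- false post-minus-pre difference = *r* × *d*

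| *r* | *d* = 0 | 0.25 | 0.5 | 0.75 | 1 |
|---|---|---|---|---|---|
| 1% | 0 | 0.4 | 0.8 | 1.2 | 1.6 |
| 3% | 0 | 1.2 | 2.4 | 3.6 | 4.8 |
| 5% | 0 | 2.0 | 4.0 | 6.0 | 8.1 |

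The false difference runs from 0 to 5.0 percentage points (5% × 1).

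**Step 3: relative size (illustration)**

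Let *f* be the share of drug-related AEs that arise between dose and consent. The missed share is *d* × *f*. Assume a true risk of 15% in both periods. The displayed pre-period risk is then 15% × (1 − *d* × *f*), and the post/pre ratio is 1/(1 − *d* × *f*).

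| *d* | *f* | Missed | Pre shown | Post shown | Ratio |
|---|---|---|---|---|---|
| 0 | any | 0% | 15.0% | 15.0% | 1.00 |
| 0.5 | 0.2 | 10% | 13.5% | 15.0% | 1.11 |
| 0.5 | 0.4 | 20% | 12.0% | 15.0% | 1.25 |

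The two illustrations agree where they overlap: 15% × 0.2 gives *r* = 3%, and with *d* = 0.5 that is 161 × 0.03 × 0.5 = 2.4 missed. The ratios apply to drug-related events only. Tables 14, 19, 20, 22 and 23 are not limited to these, so the effect there is diluted.

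**The case against.** The strongest reply is that the gap may be empty. Protocol 2.1 mentions consent before it describes usual care. Protocol 2.2.1 has usual care given to study subjects. Protocol 2.5, on subjects who have signed the ICF, foresees an AE before the first antibiotic dose. SAP 6.1.1 starts from enrolled patients and then adds the dosing requirement. Many exclusion criteria are redacted and SAP Appendix A is not shown, so a timing rule could sit there. This stands to the extent that the share dosed before consent is unknown and could be zero. None of these passages sets an order for the pre-period, however, and the blinding separates prescribing from consent.

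A reader might infer more than the documents support:

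- *Pre-period reactions are undercounted.* The documents permit this; they do not show it.
- *Reactions that occur after consent also lose attribution to study drug, so Table 21 is hit a second time.* Enrollment is defined by date, so a dose given earlier on the consent day can still count. Protocol 4.2 asks whether the drug caused the event, not which dose did, and usual care may run for days. In the ordinary same-day, multi-dose case this fails. What remains is loose wording.
- *Only one period is exposed.* That is true of each period's own study treatment. A reaction to some other antibiotic given before consent in the post-period would be missed too.
- *The ratios of 1.11 and 1.25 are estimates.* They are not. The second needs half the pre-period subjects dosed before consent and 40% of drug-related AEs in those few hours of a 44-day window.

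It is also fair that SAEs are reported descriptively, that the primary outcome is untouched, and that the bias could not create a false safety advantage for dalbavancin.

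**Conclusion.** The point holds as a possible capture gap that runs in one direction. The window is anchored at consent in both periods. Consent must precede dalbavancin, and no visible passage makes it precede the first usual-care dose. Any bias makes usual care look safer.

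The size cannot be taken from the documents. Under the assumed inputs it runs from no missed reactions to about 8 of 161, and from a ratio of 1.00 to 1.25 for drug-related events. It is exactly zero if every pre-period subject signed before the first dose. The consequence is modest, because it touches a secondary outcome and descriptive safety tables. The change is still worth making: it is cheap, it removes the gap if there is one, and it alters nothing if there is not.

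**What to change.** For SAP Tables 14 and 19–23:

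1. Start the harm window in both periods at the first antibiotic given for the ABSSSI at the index ED visit, or at ICF signature if that is earlier. Keep the current end.
2. Word the study-drug definition in Protocol section 4 and SAP 6.2.10 to match. This is a clarification, since enrollment is defined by date only.
3. For subjects dosed before signing, fill the interval from the ED record at the day 14 and day 44 chart reviews already scheduled (Protocol 3.2.1), and flag those events as retrospective.
4. Take the clock times of consent and first dose, and report by period the number consented after the first dose. If it is zero, the matter is closed.
5. Show the tables with and without the pre-consent events.

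**Cost.** Wording in Protocol 4 and 4.6 and SAP 6.2.10, plus a look at a few hours of ED record. Baseline collection already reaches back to triage, and Protocol 7.3 describes consent as covering chart review; the consent form should be checked for the hours before signature. Treatment and visits do not change. The drawback is that events taken from the chart are less complete for mild AEs than those asked about prospectively, and they would be added mainly to the pre-period. Hence the flag and the paired tables.

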4.7 Procedure for serious adverse event reporting

All SAEs that occur in a subject from the time he or she signs the ICF until the final follow-up visit will be reported to the sponsor within 24 hours of awareness of the event using the provided SAE Report Form. The completed SAE Report Form will be sent directly to the sponsor by emailing [REDACTED]. In addition to completing the SAE Report Form, each SAE will be entered on the appropriate page of the CRF. The investigator will assess the causality for each SAE.

When death occurs with an SAE, the cause of death will be reported as an SAE. “Fatal” will be reported as the outcome for these events.

The sponsor will contact the investigator, if necessary, to clarify any of the event information. The investigator will provide any follow-up information for the event to the sponsor on an updated SAE report form as soon as it becomes available.

If the investigator is notified of a SAE that occurs post-study period, that he or she wishes to report to the sponsor (e.g., an event suspected to be causally related to the study drug), the event will be reported through the process described above.

Where appropriate, if required by local regulations or procedures, the investigator will report these events to the Institutional Review Board (IRB)/Ethics Committee (EC) and/or national regulatory authority in addition to the sponsor.

4.8 Procedure for medication error reporting

Medication errors with or without an associated AE will be recorded as medication errors in the CRF. SAEs associated with medication errors will be reported to the sponsor as described in Section 5.7.

4.9 Procedures for reporting pregnancies/lactation exposure

Occurrences of pregnancy/lactation exposure in a subject should be reported within 24 hours. In cases where a pregnancy/lactation exposure occurs with a SAE, the SAE report form should be used to report the SAE and the Pregnancy Reporting form should be used to report the pregnancy.

When a pregnancy occurs without any concurrent SAE, the Pregnancy Reporting form will be submitted alone. The pregnancy will be followed through to outcome of pregnancy, including spontaneous or voluntary termination, details of the birth, and the presence or absence of any birth defects, congenital abnormalities, or maternal and/or newborn

complications. Any pregnancy discovered from the time of consent to follow-up will be reported.

4.10 Potential Hy's Law cases

Every subject that meets potential Hy's law criteria,

- ALT or AST $\geq 3 \times \text{ULN}$ AND
- Total Bilirubin $\geq 2 \times \text{ULN}$ AND
- Alkaline Phosphatase $< 2 \times \text{ULN}$

occurring anytime from the time he or she signs the ICF for the trial until the final follow up visit, investigators will notify the sponsor immediately when all the above criteria have been met. A potential Hy's law case will be sent directly to the sponsor by emailing [contact] on an AE of Special Interest Form along with the SAE Report Form as soon as possible (within 24 hours of learning of the potential Hy's law). The CRF for potential Hy's law cases will be completed within seven calendar days. Every effort to determine the cause of the liver enzyme abnormalities will be made, and close monitoring will be initiated in conjunction with the medical monitor and in accordance with the FDA "Guidance for Industry: Drug Induced Liver Injury- Pre-Marketing Clinical Evaluation" July 2009.

5 Data analysis

Frequency and proportion of subjects deemed eligible and ineligible for study enrollment based on each of the inclusion/exclusion criteria will be summarized. The frequency and proportion of subjects who successfully complete the study, withdraw, were lost-to-follow-up, and who terminated the study early, will also be reported. Subject characteristics at baseline will be summarized and described for all enrolled subjects and compared between the pre- and post-periods. Site characteristics will also be described. Descriptive statistics (count, mean, standard deviation, range for quantitative variables, and counts and percentages for categorical variables) will be reported for all outcomes. The difference in study outcomes between the pre- and post-period will be assessed using appropriate statistical methods, accounting for study site, with adequate power. The primary outcome will be tested for simple superiority, and subsequently, tested for non-inferiority with a 10% margin between the pre- and post-periods.

All analyses will be specified in a detailed statistical analysis plan (SAP) that will be prepared subsequently and before database lock. The SAP will include table and figure shells.

